Appendix B: ADRN Standard Diagnostic Criteria (Version 3.0 09May2014)

The following definitions will be used consistently throughout ADRN protocols. In children less than 4 years of age, the disease must be present for at least six months to minimize the likelihood of recruiting children with other eczematous disorders that mimic atopic dermatitis (AD).

I. Atopic Dermatitis (AD)¹**A. Active Atopic Dermatitis (AD)¹**

Participants must have AD (as defined below) within the last 3 months.

B. Inactive Atopic Dermatitis (AD)¹

Participants must have an absence of AD (as defined below) within the last 12 months.

C. Definition

Participants must have, according to medical records, or based on a careful and credible history (provided by the participant, caregiver, parent, or guardian) or by physical exam by an ADRN investigator:

1. Pruritus
2. Eczema (acute, subacute, chronic)
 - a. Typical morphology and age-specific patterns which include:
 - i. Facial, neck, and extensor involvement in infants and children
 - ii. Current or prior flexural lesions in any age group
 - iii. Sparing groin and axillary regions
 - b. Chronic or relapsing history
 - c. Most participants will have the following clinical associations that add support to the diagnosis:
 - i. Early age at onset
 - ii. Atopy
 1. Personal and/or family history
 2. Immunoglobulin (IgE) reactivity
 - iii. Xerosis

Participants may have the following clinical associations which help to suggest the diagnosis of AD but are too non-specific for defining or detecting AD for research or epidemiological studies:

1. Atypical vascular responses (e.g., facial pallor, white dermographism, delayed blanch response)
2. Keratosis pilaris/hyperlinear palms/ichthyosis
3. Ocular/peri-orbital changes
4. Other regional findings (e.g., peri-oral changes/peri-auricular lesions)
5. Peri-follicular accentuation/lichenification/prurigo lesions

References

¹Eichenfield F, Hanifin J, Luger T, Stevens S, Pride H. Consensus Conference on Pediatric Atopic Dermatitis. J Am Acad Dermatology 2003;49:1088-95.

1 LIST OF ABBREVIATIONS

AD	Atopic Dermatitis
ADR	Adverse Drug Reaction
ADRN	Atopic Dermatitis Research Network
AE	Adverse Event
AR	Adverse Reaction
CBC	Complete Blood Count
CFR	Code of Federal Regulations
CFU	Colony Forming Unit
CoNS	Coagulase Negative Staphylococcal Species
CPC	Clinical Product Center
CRA	Clinical Research Associate
CRSwNP	Chronic rhinosinusitis with nasal polyps
CTCAE	Common Terminology Criteria for Adverse Events
DAIT	Division of Allergy, Immunology, and Transplantation
DNA	Deoxyribonucleic Acid
DoR	Delegation of Responsibility Log
DSMB	Data Safety Monitoring Board
EASI	Eczema Area and Severity Index
eCRF	Electronic Case Report Form
EDC	Electronic Data Capture
EO	Exploratory Objective
EoE	Eosinophilic Esophagitis
FDA	Food and Drug Administration
FLG	Filaggrin
GCP	Good Clinical Practice
GLM	Generalized Linear Model
GWAS	Genome-wide Association Study
HIV	Human Immunodeficiency Virus
IGA	Investigator Global Assessment
IgE	Immunoglobulin E
IL	Interleukin
IRB	Institutional Review Board
ISR	Injection Site Reaction

JAK	Janus kinase
mAb	Monoclonal Antibody
MOP	Manual of Procedures
NBUVB	Narrowband Ultraviolet B
NCI	National Cancer Institute
NESS	Nottingham Eczema Severity Score
NIAID	National Institute of Allergy and Infectious Diseases
NIH	National Institutes of Health
OHRP	Office for Human Research Protections
PCR	Polymerase Chain Reaction
PI	[Site] Principal Investigator
PP-NRS	Peak Pruritus Numerical Rating Scale
PUVA	Psoralen and Ultraviolet A
Q2W	Every other week
Q4W	Every 4 weeks
RNA	Ribonucleic Acid
S. aureus	Staphylococcus aureus
SACCC	Statistical and Clinical Coordinating Center
SAE	Serious Adverse Event
SAP	Statistical Analysis Plan
SAR	Suspected Adverse Reaction
SCORAD	Scoring Atopic Dermatitis
SO	Secondary Objective
SOP	Standard Operating Procedure
STS	Skin tape strip
TAA	Target Area Assessment
TCS	Topical Corticosteroids
Th	T Helper
TSB	Tryptic Soy Broth
US	United States
UVA1	Ultraviolet A1
UVB	Ultraviolet B
WGCNA	Weighted Gene Co-expression Network Analysis
WTS	Whole Transcriptome Sequence

2 PURPOSE OF THE ANALYSES

2.1 Primary objective

To determine if the type 2-high non-lesional skin (skin tape) endotype is associated with current mild versus moderate-to-severe AD disease

2.2 Secondary objectives

1. To determine how gene expression in the skin (skin tape) differs between non-AD participants and those with current mild or moderate-to-severe AD disease
2. To determine how gene expression in the skin (skin tape) changes with standard-of-care treatment (two timepoints) among the study outcome groups: (1) topical steroid responders, (2) dupilumab responders, (3) dupilumab non-responders, (4) non-AD, and (5) long-term dupilumab participants

2.3 Exploratory objectives

Not covered in this SAP, please refer to a separate Exploratory SAP.

3 PROTOCOL SUMMARY

This is a multi-center, longitudinal study that will characterize the gene expression profiles and transcriptomic endotypes that underlie mild and moderate-to-severe AD and will determine changes in these expression patterns and endotypes in response to standard-of-care treatment as delineated in the protocol. The primary objective of this study is to determine whether the type 2-high non-lesional skin endotype is associated with current mild versus moderate-to-severe AD disease.

4 ANALYSIS SAMPLES

4.1 Primary Endpoints

Non-lesional skin tape transcriptome at Day 7 (long-term dupilumab participants excluded)

4.2 Secondary Endpoints

1. Non-lesional and lesional skin tape transcriptome at Day 7 and Day 168-224 (long-term dupilumab participants excluded) [Secondary Objective (SO)1]
2. Non-lesional and lesional skin tape transcriptome at Day 7 and Day 168-224 [SO2]

4.3 Exploratory Endpoints

Please refer to the Exploratory SAP.

5 ESTIMANDS FOR PRIMARY AND KEY SECONDARY EFFICACY ENDPOINTS

5.1 Primary Estimand

The primary estimand is the odds ratio describing the difference in frequency of mild (Day 7 EASI ≤ 7) vs. moderate-to-severe (Day 7 EASI > 7) AD between those with and without the type 2 endotype, as defined using gene expression in the non-lesional Day 7 skin tape transcriptome. The analysis will be carried out separately for the children (6-17 years old) and adults (18+ years old) populations in the study. Similarly, we will estimate the odds ratio for the change in the odds of having mild vs. moderate-to-severe AD associated with 1 unit increase in the geometric mean levels of type 2 gene expression from the non-lesional Day 7 skin tape transcriptome (again, separately in children and adults).

5.2 Secondary Estimands

The first of the two secondary estimands is the difference in mean gene expression from non-lesional skin tape transcriptome at Day 7, and separately at Day 168-224, between Non-AD vs. Mild DNAD and Non-AD vs. Moderate-to-severe DNAD children (6-17 years old), and separately adults (18+ year olds), enrolled in this study.

The second of the two secondary estimands is the mean change in normalized gene expression between Day 7 and Day 168-224 non-lesional skin tape transcriptomes, among topical steroid responders, dupilumab responders, dupilumab non-responders, non-AD, and long-term dupilumab responders in children (6-17 years old), and separately in adults (18+ year olds) enrolled in this study.

6 STUDY SUBJECTS

6.1 Study Subject Summary

The study population consists of children and adults with mild and moderate-to-severe AD, as well as children and adults with no AD. The total sample size will be approximately 600 children and adults (200 children and 400 adults). Formal intent-to-treat and per protocol populations do not apply to this study. Because we want a balanced population with regard to age, sex, and race/ethnicity between the three enrollment groups, we will monitor these variables during the enrollment period. Any detected skews accruing during enrollment will be addressed by instructing sites to target unrepresented groups. When assigning participants as child or adult, the age at baseline will be used (6-17 years at baseline = child; ≥ 18 at baseline = adult).

6.2 Disposition of Subjects

Study participants, whether child or adult, will be allocated to the following diagnostic groups prior to analysis:

- I. *Non-AD*
Participants never diagnosed with AD.
- II. *Dupilumab-naïve AD participants*
AD participants never taking dupilumab.

There are two possible AD severity groups:

1. Mild AD (EASI ≤ 7 at analysis timepoint)
2. Moderate-to-severe AD (EASI > 7 at analysis timepoint)

There are three possible outcome groups:

1. Topical steroid responders: Those on topical steroid who never obtain an EASI score > 7 by the 12-Week Steroid Assessment visit (EASI score > 7 obtained after that point will lead to early study termination).
2. Dupilumab responders: Steroid non-responders on dupilumab who obtain an EASI score ≤ 7 at the 15-Week Dupilumab Assessment visit (regardless of EASI scores obtained before or after that visit).
3. Dupilumab non-responders: Those on dupilumab who fail to obtain an EASI score ≤ 7 at the 15-Week Dupilumab Assessment visit (regardless of EASI scores obtained before or after that visit).

- III. *Long-term dupilumab AD participants*
AD participants already on dupilumab (for ≥ 4 months) at the start of the study. These patients will continue dupilumab treatment as prescribed by their physician outside of the study.

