3.1.1 DNAD Participants

On Day 7, DNAD participants will begin applying triamcinolone 0.1% ointment (provided by the study) twice daily to the specified target area. Additionally, DNAD participants will apply triamcinolone 0.1% ointment (non-sensitive regions)/ hydrocortisone 2.5% ointment (sensitive regions) twice daily to active lesions on non-target skin.

On Day 35, DNAD participants will return for a 4 Week Steroid Assessment, where response to triamcinolone will be evaluated at the target site by TAA and targeted EASI scoring, and overall management of AD body-wide by topical steroid/moisturizer treatment will be evaluated by EASI score. DNAD participants who have an inadequate body-wide response to topical steroid/moisturizer treatment (EASI > 7) will be designated as "topical steroid non-responders" and will begin treatment with dupilumab. DNAD participants with EASI ≤ 7 will be designated as "topical steroid responders" and will continue to apply triamcinolone/hydrocortisone to active lesions.

Topical Steroid Responders

After the 4 Week Steroid Assessment, topical steroid responders will discontinue applying triamcinolone 0.1% ointment to non-lesional skin on the target area. Topical steroid responders will begin to apply triamcinolone 0.1% ointment (non-sensitive regions)/ hydrocortisone 2.5% ointment (sensitive regions) once or twice daily, per clinician discretion, to active lesions body-wide. They will return for up to three additional scheduled visits prior to their End of Study Visit: an Optional Steroid Assessment, 12 Week Steroid Assessment, and a 19 Week Steroid Assessment.

If symptoms worsen at any time between planned study visits, participants can be scheduled for an Unscheduled Visit. If their EASI score is > 7 at any of the scheduled or unscheduled visits beginning at the 4 Week Steroid Assessment through the 12 Week Steroid Assessment, they will be designated as a “topical steroid non-responder” and will begin treatment with dupilumab. After the 12 Week Steroid Assessment, if the participant’s EASI score is > 7 at any point, they will be withdrawn from the study.

[figure not shown]

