8 GENERAL ANALYSIS AND REPORTING CONSIDERATIONS

8.1 Analysis Visits

The Day 7 Visit – for all relevant clinical and outcome groups, the Day 7 visit pertains to the 1st Week Clinical Assessment Visit that occurs 7 days (± 3 days) after the Baseline Assessment (Day 0) at study enrollment.

The End of Study Assessment (Day 168-224) Visit – for Non-AD, Topical Steroid Responders, and Long-term Dupilumab participants, their End of Study Assessment Visit occurs 168 days (± 3 days) after the Baseline Assessment (Day 0) at study enrollment. For Topical Steroid Non-Responders, their End of Study Assessment Visit occurs 133 days (130-136 days) after Dupilumab Initiation, which can occur any time between 35 days (-3, +6 days) and 91 days (± 3 days) after the Baseline Assessment (Day 0) at study

enrollment depending on when the participant obtains the qualifying EASI score (> 7) for initiating Dupilumab. Hence, the End of Study Assessment Visit can range from Day 168 to 224.

Unscheduled Visit - participants may be asked to return to the clinic for Unscheduled Visits, as needed, to provide additional skin swabs, STS, and/or skin biopsies for studies, or if samples are lost or destroyed, or if insufficient yields were obtained at a previous study visit. Thus, for the purposes of the analyses described in this SAP, the STS samples obtained at an unscheduled visit that occurred after the Day 7 or End of Study Assessment visits may be used for analysis instead if the samples obtained at the scheduled visits were lost, destroyed, or yielded insufficient gene expression.

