To investigate changes in skin gene expression due to standard-of-care treatment as delineated in the protocol and how these changes may differ with study outcome groups (i.e., groups based on treatment regimen and response), we will model gene expression at both Day 7 and End of Study (Day 168-224) Visits using linear mixed models. Gene expression data will be normalized using the VST method. Models will include fixed effect variables for visit, study outcome group (topical steroid responders, dupilumab-naïve responders, dupilumab-naïve non-responders, non-AD, and long-term dupilumab participants), and visit x

study outcome group interaction, along with relevant covariates and a random intercept for each participant to account for pairing of Day 7 and End of Study samples. Among the covariates, there will be a binary variable that further distinguishes topical steroid responders who had mild AD to begin with since baseline (set covariate = 1) versus those who actually improved from having moderate-to-severe AD at baseline (set covariate = 0) in order to consider them as “true” topical steroid responders to compare with among the other outcome groups in the model (all remaining groups would set covariate = 0 as well). Using this model, we will examine responses to standard-of-care treatment as delineated in the protocol by contrasting Day 7 and End of Study Assessment Visits within outcome groups. We will also examine differences in response to standard-of-care treatment between any two outcome groups by testing the interaction term for visit effect in one outcome group versus another.

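### SAP 6.2 gives the topical steroid responder rule no start point, so a protocol responder with an unscheduled EASI above 7 between steroid initiation and the 4 Week visit has no outcome group in Secondary Objective 2

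*SAP*

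**What the plan says.** SAP 6.2 lists three outcome groups for dupilumab-naïve participants. Topical steroid responders are "Those on topical steroid who never obtain an EASI score > 7 by the 12-Week Steroid Assessment visit". The other two groups both require dupilumab: "Steroid non-responders on dupilumab who obtain an EASI score ≤ 7 at the 15-Week Dupilumab Assessment visit" and "Those on dupilumab who fail to obtain an EASI score ≤ 7 at the 15-Week Dupilumab Assessment visit". Each of these two entries adds that scores at other times are irrelevant. The steroid entry adds nothing of the kind.

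Protocol 3.1.1 makes the first classification at Day 35: "DNAD participants with EASI ≤ 7 will be designated as" topical steroid responders. They lose that status if EASI exceeds 7 "at any of the scheduled or unscheduled visits beginning at the 4 Week Steroid Assessment through the 12 Week Steroid Assessment". Protocol 8.5 and 8.6 give the same window, and an Appendix A footnote confirms that the initial classification rests on the 4 Week score. SAP 8.1 places dupilumab initiation between the Day 35 and Day 91 visits, with their windows.

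SAP 9.2.2 adds a covariate that separates responders who were mild from baseline "versus those who actually improved from having moderate-to-severe AD at baseline". It treats the second set as the genuine responders.

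**The concern.** Outcome group is the grouping variable for Secondary Objective 2. It defines SAP 9.2.2 models 1 and 12, which answer that objective, and all the supporting models. The rule that assigns it should therefore put every dupilumab-naïve participant who completes the study in exactly one group.

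With *never* and *by* but no start, SAP 6.2 does not do this. Take a participant whose EASI is above 7 at a flare visit on about Day 20, and at or below 7 from the 4 Week through the 12 Week visit. Under the protocol this is a responder who continues on steroid. Under the wording of SAP 6.2 the participant is not a responder, and without dupilumab cannot enter either of the other groups. Whoever programs the variable would have to choose between dropping this person and overriding the text, possibly after data have been seen.

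**Working it through.** **1. Which early scores are in doubt**

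- *Baseline.* SAP 9.2.2 keeps participants who were moderate-to-severe at baseline, hence above 7, in the responder group. Baseline scores therefore cannot disqualify.
- *Day 7.* Steroid is first distributed and started at this visit (protocol 3.1.1 and 8.4), so the Day 7 EASI precedes steroid use. SAP 6.2 speaks of people on topical steroid, which points to later scores.
- *After Day 7 and before the 4 Week visit.* The visit table in protocol 8.13 and the Appendix A schedule contain no EASI here. Protocol 8.12 allows one at an unscheduled visit. Nothing in the SAP says whether such a score counts towards the responder definition.
- *4 Week through 12 Week.* Protocol and SAP agree.

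Only the third interval is left open.

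**2. The projected group sizes confirm the intent**

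Inputs from protocol 13.7.1: 160 adults and 80 children moderate-to-severe, 100 adults and 50 children mild; steroid failure 50% and 5%.

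Responders = moderate-to-severe n × 0.50 + mild n × 0.95

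- Adults: 160 × 0.50 + 100 × 0.95 = 80 + 95 = 175 (stated 175).
- Children: 80 × 0.50 + 50 × 0.95 = 40 + 47.5 = 87.5 (stated 87).

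The stated sizes are reached only if 80 adults and 40 children who start above 7 are counted as responders.

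**3. Reproducing the stated detectable fold changes**

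Inputs from protocol 13.7.1: α = 0.05/10,000 = 0.000005, CV 0.4, 10 reads per gene, power 80%. The RNA-seq power formula is

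fold change = exp{ √[ 2 (z₁₋α/₂ + z₀.₈)² (1/depth + CV²) / n ] }

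Two-sided z values are 4.565 and 0.842 (sum 5.406), and 1/10 + 0.16 = 0.26. So 2 × 5.406² × 0.26 = 15.2, and fold change = exp(√(15.2/n)).

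- n = 175: 1.34 (stated 1.34); with 20% dropout, 1.39 (stated 1.39).
- n = 87: 1.52 (stated 1.52); with 20% dropout, 1.60 (stated 1.60).

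A one-sided α gives 1.33 and 1.50, so the table is two-sided. The other eight rows of Table 13.7.1.3 also reproduce to two decimals.

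**4. Effect of the unresolved case**

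The share of responders with an unscheduled EASI above 7 in this interval is not in the documents. A range is assumed, and those people are removed from the target sample sizes.

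| Assumed share | Adults without a group | Fold change, adults | Children without a group | Fold change, children |
|---|---|---|---|---|
| 0% | 0 | 1.34 | 0 | 1.52 |
| 1% | about 2 | 1.34 | about 1 | 1.52 |
| 5% | about 9 | 1.35 | about 4 | 1.54 |
| 10% | about 18 | 1.36 | about 9 | 1.55 |

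**The case against.** The best defence is that the sentence is shorthand and the start point can be found elsewhere. The protocol creates responder status only at the 4 Week visit, so before then there is no status to lose. SAP 8.1 ties the qualifying score to the Day 35 to Day 91 interval. The protocol itself sometimes names only the end of the window (synopsis treatment description, section 8.8 and an Appendix A footnote), where the context is participants already classified. SAP 6.2 cannot be read strictly in any case: it heads the dupilumab-naïve group as never having taken dupilumab, and then lists two subgroups who are on it.

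Most of this stands as evidence of intent. It does not mend the definition. SAP 8.1 says when dupilumab may start, not which scores remove someone from the responder group. The *never* in SAP 6.2, next to two entries that expressly set other scores aside, invites the opposite reading.

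A reader might go further and infer that every pre-treatment score counts. Then 80 of 175 adults and 40 of 87.5 children (46% each) would leave the group and no genuine responders would remain for the SAP 9.2.2 covariate. The detectable fold change would rise to exp(√(15.2/95)) = 1.49 in adults and exp(√(15.2/47.5)) = 1.76 in children. The documents do not support this as an expected result: steps 1 and 2 of the working rule it out for baseline scores and argue strongly against it for Day 7.

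Nor do they show that the people left without a group would be the more severe responders. Protocol 8.12 allows unscheduled visits for flares, but also to replace lost or low-yield samples, and no data describe who attends.

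**Conclusion.** The point holds in a narrow form. SAP 6.2 as written conflicts with the protocol's classification window and, taken literally, with SAP 9.2.2. After reading the documents together, one kind of participant remains misclassified: the protocol responder with an unscheduled score above 7 after steroid initiation and before the 4 Week visit.

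Few people are likely to be affected, because no EASI is scheduled in that interval. The range in step 4 rests on an assumed share of 1% to 10%, and at its upper end power barely changes. The reason to act is that the rule for the main grouping variable of Secondary Objective 2 is incomplete and disagrees with the protocol. It is not that the sample for that objective is lost.

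**What to change.** Align the SAP 6.2 outcome group with the protocol classification. Suggested text: a topical steroid responder is a dupilumab-naïve participant on topical steroid with no EASI above 7 at any scheduled or unscheduled visit from the 4 Week through the 12 Week Steroid Assessment; scores before the 4 Week Steroid Assessment do not count for this outcome group.

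The cost is one sentence in the SAP. It brings SAP 6.2 into line with protocol 3.1.1, 8.5 and 8.6, SAP 9.2.2 and the group sizes in Table 13.7.1.3. It changes only how participants are grouped for analysis: no treatment rule, visit, sample or sample size is altered.

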7 STUDY OPERATIONS

7.1 Protocol Deviations

Protocol Deviation – The investigators and site staff will conduct the study in accordance with the protocol; no deviations from the protocol are permitted. Any change, divergence, or departure from the study design or procedures constitutes a protocol deviation. As a result of any deviation, corrective actions will be developed by the site and implemented promptly.

Major Protocol Deviation (Protocol Violation) - A Protocol Violation is a deviation from the IRB approved protocol that may affect the participant's rights, safety, or well-being and/or the completeness, accuracy, and reliability of the study data. In addition, protocol violations include willful or knowing breaches of human participant protection regulations or policies; any action that is inconsistent with the NIH Human Research Protection Program's research, medical, and ethical principles; and any serious or continuing noncompliance with federal, state, local or institutional human participant protection regulations, policies, or procedures. Examples of Major Protocol Deviations are described in the study MOP.

Non-Major Protocol Deviation - A non-major protocol deviation is any change, divergence, or departure from the study design or procedures of a research protocol that does not have a major impact on the participant's rights, safety or wellbeing, or the completeness, accuracy, and reliability of the study data.

